Heart Failure (HF) is a major public health issue because the disease affects 1-2% of the Western population[1] and the lifetime risk of HF is 20% [1]. HF is responsible for 1-2% of all healthcare expenditures and 5 % of all hospital admissions [2]. The cornerstone in the medical treatment of chronic HF is a combination of ACE-inhibitors/ATII-receptor antagonists, beta-blockers and mineralocorticoid receptor antagonists [3]. Despite major improvements in the management and care of patients with HF, the 1-year mortality in patients with HF is 13 % [4] and >50% of HF-patients is admitted during a 2.5 year period [5]. Furthermore patients with HF have markedly decreased physical capacity and quality of life. Thus, there is a need for new treatment modalities in this group of patients.

Ketone bodies are produced in the liver and are of vital importance in the human body for energy generation in the heart and brain during fasting, exercise and severe illness [9, 10]. However, ketosis can be safely obtained using dietary supplements [10-12] and can increase exercise capacity in athletes [6]. The most important ketone bodies are 3-OHB and acetoacetate. Recently, it was demonstrated that patients with severe HF have increased myocardial utilization of the ketone body 3-hydroxybutyrate (3-OHB) [7]. It has been hypothesized that ketone bodies may act as “superfuel” for the failing heart [8]. In support of this, the glucose-lowering SGLT-2 inhibitor empagliflozin reduces the risk of hospitalizations and cardiovascular death in diabetic patients with HF [9] and also increases circulating levels of 3-OHB [10].

We have shown, using positron emission tomography, that ketone body infusion reduces myocardial glucose uptake and increases myocardial blood flow in healthy subjects [11]. Data from another study conducted by our group show a 40% increase in cardiac output during infusion of 3-OHB [12]. The mechanisms behind these marked hemodynamic effects are presently unknown, but could involve prostaglandin-release. 3-OHB is the endogenous ligand for the G protein-coupled receptor hydroxy-carboxylic acid 2 (HCA2) receptor. This receptor has downstream effects on cAMP and systemic effects via release of prostaglandins [13]. Presently there are no data on the clinical cardiovascular and metabolic effects of long - or short term oral ketone-supplementation in patients with chronic HF.

2 Hypotheses

Exercise capacity and cardiac function can be improved in patients with chronic HF by increasing circulation ketone bodies. This can be achieved through a dietary supplement of 3-OHB.

3 Objectives

- 1: To determine uptake kinetics of oral 3-OHB supplements in patients with chronic HF.
2. Furthermore to investigate acute pharmacodynamic effects (i.e. hemodynamic effects) of oral 3-OHB intake by two different ketone-supplements.
- 3: To investigate the effect of 4 weeks modulation of circulating ketone body levels on cardiac function and exercise capacity in chronic HF patients.

4 Design and endpoints

The study consists of one pilot study (KETO-KINETICS) and one main study (KETO-CHF) with a hemodynamic substudy and a metabolic substudy. . The purpose of the pilot study is 1) to establish uptake kinetics and 2) acute hemodynamics of two oral ketone dietary supplements, and 3) differentiate acute and chronic effects of oral ketone supplementation. There will be separate participant informations and consent forms for the substudies. Thus participants can opt only to participate in one substudy if they prefer. The study days are outlined in table 1-3.

Original protocol title: *Modulation of circulating levels of the ketone body 3-hydroxybutyrate in patients with chronic heart failure: Cardiovascular and metabolic effects*

[name], Læge, PhD-studerende, Afd. for Hjertesygdomme, Aarhus Universitetshospital Skejby, Aarhus, Denmark

Scientific Committee ref.: 1-10-72-362-18

KETO-KINETICS: KETO-CHF pilot study:

Design: 10 patients are studied after an overnight fast, in random order on 3 visits, during a) oral intake of 36 g Perfect Keto Oral 3-OHB supplement, b) oral intake of 25 g HVMN Ketone Ester, and c) during a placebo isocaloric drink (similar energy content as the 36 g 3-OHB dose, containing 1:1:2 mixtures of dextrose, fructose, and maltodextrin) [6].

Endpoints: Cardiac output, venous 3-OHB levels, LVEF, LV global strain.

Methods: Swan-Ganz Monitoring, Echocardiography, ECG and blood pressure will be recorded hourly. 3-OHB levels are measured by venous blood samples every 60 minutes. Sampling will be performed hourly from 1 hour before till 5 hours after oral intake.

KETO-CHF: Randomized, double blind crossover study with 20 stable chronic HF patients.

Design: Patients are studied after 4 weeks of oral 3-OHB three times daily (36 g "Perfect Keto Base" or 25g HVMN Ketone Ester depending on the outcome of KETO-KINETICS three times) and 4 weeks isocaloric placebo-drink. Both "Perfect Keto Base" (Perfect Keto, Glendale Heights, IL, USA) and HVMN Ketone Ester (HVMN, San Francisco, CA, USA) are a commercially available ketone diet supplements.

Endpoints: 1) Cardiac output (primary), mixed venous saturation (SVO2), pulmonary wedge pressure 2) Rest/Peak Exercise Echocardiography (LVEF, Global Strain), 3) Cardiopulmonary exercise test, 4) Whole-body substrate metabolism, insulin signalling and lipolysis.

Methods: Swan-Ganz monitoring, echocardiography, exercise capacity, whole-body glucose, FFA and protein metabolism will be examined using isotope tracer techniques. Furthermore, muscle biopsies will be drawn for studies of insulin signalling and lipolysis (chapter 5).

[figure not shown]

Figure 1: Patient Inclusion flowchart

Table 1: Study Visits Overview

Visit	V0 Screening	Teleph. Contact	V1 Randomizat ion	V2 Hemodynamic examination 1	V3 Metabolic Examinations 1	V4 Hemodynamic examinations 2	V5 Metabolic Examinations 2
Time (Days, Weeks, Months)	-4W to 0	-3½ W-0W	0	3-5W	3-5W	10-12W	10-12W
General							

Original protocol title: *Modulation of circulating levels of the ketone body 3-hydroxybutyrate in patients with chronic heart failure: Cardiovascular and metabolic effects*

[name], Læge, PhD-studerende, Afd. for Hjertesygdomme, Aarhus Universitetshospital Skejby, Aarhus, Denmark
Scientific Committee ref.: 1-10-72-362-18

Informed consent	X						
In-and exclusion criteria	X		X				
Relevant medical/surgical history			X				
Relevant concomitant medication (1)			X				
Randomize patient			X				
Study medication							
Delivery	(Trial period)		X				
Crossover					X		
Clinical assessment							
NYHA class			X	X	X	X	X
Height			X				
Weight			X	X	X	X	X
Echocardiography				X		X	
Swan-Ganz Monit.				X		X	
CPX-test				X		X	
Whole-Body Metabolism					X		X
Blood Samples				X	X	X	X
Muscle Biopsies					X		X
ECG			X	X		X	
Blood pressure, heart rate	X		X	X	X	X	X
Safety							
Reporting of: -Endpoints -SUSARs -selected AEs		X	X	X	X	X	X

Table 2: Hemodynamic study day overview

Time	07.30	08.30	09.15	09.30	10.30	10.50	11.10	11.30	12.30
Arrival			X						
Swan Ganz				X					
Exercisetest						X			
Blood Samples				X		X	X	X	X
Echocardiography				X		X	X	X	X
Invasive measurements				X		X	X	X	X

Original protocol title: *Modulation of circulating levels of the ketone body 3-hydroxybutyrate in patients with chronic heart failure: Cardiovascular and metabolic effects*

[name], Læge, PhD-studerende, Afd. for Hjertesygdomme, Aarhus Universitetshospital Skejby, Aarhus, Denmark
Scientific Committee ref.: 1-10-72-362-18

3-OHB/placebo ingestion	x
End of study day	x

Table 3: Metabolic study day overview

Time	07.30	08.30	09.30	10.30	11.30	12.30	13.30	14.30
Arrival		x						
Basal period								
3-OHB sipping								
3-OHB sipping + Clamp								
[3- ³ H]Glucose-Infusion								
[9,10- ³ H]Palmitate-infusion								
Muscle Biopsy			x					x
Blood samples	x		x	x	x	x	x	

5 Methods

5.1.1 Swan-Ganz Monitoring:

This is a standard procedure at the clinical research site and will be performed in a dedicated cardiac catheter lab with experienced physicians. Standard triple-lumen Swan-Ganz thermister and balloon-tipped catheters will be used. Catheters will be introduced using the internal jugular vein, using ultrasound guidance, and advanced using pressure waveform and fluoroscopy into the pulmonary artery. Cardiac output will be measured using the thermodilution method.

Measurements will be made at rest, during peak exercise and post-exercise.

5.1.2 Rest/Peak Exercise Echocardiography:

We intend to use a GE VIVID 7 or 9E system (GE Medical System, Horten, Norway) with a 2.5-MHz transducer for transthoracic echocardiography. For image analysis EchoPAC (GE-Vingmed Ultrasound, Horten, Norway) will be used. All measurements will be the averaged over 3 consecutive heart cycles in end-expiration. 2D echocardiography will be performed according to national guidelines [14]. In case of poor image quality, a contrast agent (SonoVue/Optison) will be used to opacify the left ventricle (LV) [15, 16]. Regarding LV measurements, the following parameters will be recorded: 2D [16], regional wall motion score (16 segment model), LVEDV and LVESV, left atrial volume, tissue Doppler study of the mitral annulus and LV strain and strain-rate[17].

5.1.3 Whole-body metabolism:

Glucose metabolism is determined by isotope dilution technique with constant infusion of [3-³H] glucose (12 µCi / min) from two hours before and 60 minutes after intake of ketones or isocaloric placebo.

FFA Turnover is determined by isotope dilution technique with 2 times 1-hour constant infusion of [9,10-³H] palmitate (0.3 µCi / min, totalling 36 µCi) before and 60 minutes after oral intake. Blood samples to determine FFA concentration and specific activity will be taken at baseline and after 30, 40, 50 and 60 minute infusion. Plasma FFA (palmitate) concentration and specific activity are determined by HPLC[18].

Original protocol title: *Modulation of circulating levels of the ketone body 3-hydroxybutyrate in patients with chronic heart failure: Cardiovascular and metabolic effects*

[name], Læge, PhD-studerende, Afd. for Hjertesygdomme, Aarhus Universitetshospital Skejby, Aarhus, Denmark

Scientific Committee ref.: 1-10-72-362-18

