5.1.4 Muscle biopsies

Samples are taken from the vastus lateralis by sterile technique. Proteins involved in insulin-signalling and lipolysis will be determined by Western Blot technique.

5.1.5 Cardiopulmonary Exercise Test:

Cardiopulmonary exercise capacity will be performed using a staged bicycle exercise test with measurements of oxygen consumption and carbon dioxide excretion. After resting measurements are obtained patients will start exercising at 0 watts and using 3 minute intervals increase to 20 watts and then with 10 watt increments every 3 minutes until peak exercise (Borg > 18). At each level of exercise hemodynamic and echocardiographic measurements will be recorded. A preliminary exercise test will be performed prior to the baseline study to make the patient familiar with the procedure.

5.1.6 Blood samples:

Venous blood samples for measurements of plasma insulin, free fatty acids, glucose, ketone bodies, lactate, haemoglobin, P-Na⁺, P-K⁺. Will be measured three times during each visit P-LDL, P-HDL and P-Cholesterol (total), prostaglandin E2, I2, F2 α , thromboxane A, erythropoietin, thrombopoietin and granulocyte stimulating factor will be measured twice during the pilot study and the hemodynamic study days.

6 Power calculation and statistics

Power calculations

In the pilot study we plan to include 8 patients. However, if necessary because of drop-outs or missing values up to 10 patients will be included.

Coefficiency of variation (CV) regarding Cardiac output by pulmonary artery catherization is determined to be 4 % [19]. By enrolling 8 patients in the KETO-KINETIC pilot study, we will be able to detect a relative difference of 6% with a power of 90% and a two-sided significance level of 5%. In the KETO-CHF study by enrolling 20 patients in the hemodynamic examinations, and allowing up to 20 % missing values, we will be able to determine a relative difference of 4 %, and thus detect changes related to clinical outcome [20], with a power of 90% and a two-sided significance level of 5%.

In the metabolic studies, previous studies have shown an SD of the difference of 8% and an effect size of 10%. With power and significance level as described above a sample size of 8 patients are needed. To allow 20% missing values 10 patients will be included in the metabolic studies.

Reporting of endpoints:

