For these studies normally distributed variables will be presented as mean \pm SD. Non-parametric statistics and appropriate log-transformation will be performed if assumption of normality is not met. A two-tailed p value of 0.05 or less will be considered statistically significant.

Differences will be compared by appropriate paired statistical tests. Regression analysis will be performed and correlation coefficients will be presented when appropriate.

7 Patient recruitment

Patients with stable HF will be recruited from the outpatient HF clinic at Aarhus University Hospital.

Inclusion criteria: Chronic HF: NYHA class II-III, left ventricular ejection fraction (LVEF) <40%

Exclusion Criteria: Diabetes or HbA1c >48 mmol/mol, significant cardiac valve disease, severe stable angina pectoris, severe comorbidity as judged by the investigator, inability to give informed consent

Original protocol title: *Modulation of circulating levels of the ketone body 3-hydroxybutyrate in patients with chronic heart failure: Cardiovascular and metabolic effects*

[name], Læge, PhD-studerende, Afd. for Hjertesygdomme, Aarhus Universitetshospital Skejby, Aarhus, Denmark
Scientific Committee ref.: 1-10-72-362-18

Recruitment and informed consent

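### KETO-KINETICS secures neither balance over visit position nor a visit term, so any visit effect would add noise (not bias) to comparisons of three drinks in 8 to 10 patients

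*Combined protocol and SAP*

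**What the plan says.** Section 4 describes the pilot as a three-drink crossover (two ketone products and an isocaloric placebo): "10 patients are studied after an overnight fast, in random order on 3 visits". Section 6 gives the size as "In the pilot study we plan to include 8 patients", with the allowance that "because of drop-outs or missing values up to 10 patients will be included". It takes a 4% coefficient of variation for cardiac output and claims 90% power, two-sided 5%, for a 6% relative difference with 8 patients.

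On analysis, Section 6 says "Differences will be compared by appropriate paired statistical tests". It names no visit (period) or sequence term. Nothing states how the order is generated, which sequences are used, or whether each drink appears equally often at each visit. Section 4 schedules a sample one hour before intake at every pilot visit, but does not say whether change from it is analysed. Section 4 also makes the main-study product depend on the pilot's outcome.

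For the metabolic substudy of KETO-CHF, Section 6 says "To allow 20% missing values 10 patients will be included in the metabolic studies". The main study has 20 patients, and nothing is said about how the two sequences fall within the metabolic group.

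**The concern.** A first catheterisation day may differ from later ones whatever the patient drinks. If each patient's order is drawn independently, a list of 8 or 10 will usually cross drink with visit position unevenly, and part of any visit effect then enters each drink contrast. Only one list is used, so its particular imbalance stays in the one result that informs the choice of product. An unadjusted paired test also leaves the visit effect in the within-patient differences, where it inflates the error. Both losses can be avoided within the planned number of patients.

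**Working it through.** **1. The plan's own figure.** Paired t-test, two-sided 5%, 6% difference, 8 patients:
- 4% read as the SD of the paired difference: power 95.1%, detectable difference at 90% power 5.4%, 7 patients needed. The stated 8 patients and 6% fit this reading with rounding.
- 4% read as the SD of a single visit (SD of the difference 4 × √2 = 5.66%): power 73.1%, detectable difference 7.6%, 12 patients needed. This does not reproduce the plan.
- An SD of the difference of 4.5% gives 89.6%, the stated 90%. It is used below, so that the starting point is the plan's own power.

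**2. How uneven a random list is.** The chance that some drink comes first in 5 or more of 8 patients is 3 × P(Binomial(8, 1/3) ≥ 5) = 3 × 577/6561 = 26%. All positions are as balanced as 8 patients allow in only about 6% of random lists.

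**3. SD of a drink contrast.** Let the first visit shift cardiac output by s (assumed). For drinks A and B, the shift enters a patient's difference as +s, −s or 0, each with probability 1/3, so its variance is (2/3)s² and its mean is zero. At s = 5%:
- Random order, n = 8: √[(20.25 + 16.67)/8] = 2.15. At n = 9: √(36.92/9) = 2.03.
- Latin blocks, n = 9: first visits are 3:3:3, the shift cancels, and the SD is √(20.25/9) = 1.50.
- Latin blocks, n = 8: first visits are 3:3:2. Two times in three the contrast is off by 5/8 = 0.625, so the SD is √(20.25/8 + (2/3) × 0.625²) = 1.67.

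Simulation gives 2.17 and 1.68 at n = 8, and 2.03 and 1.49 at n = 9.

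**4. Why balance alone does not return the power.** With 9 balanced patients the shift cancels from the mean but not from the spread. Six of the nine differences carry ±5, which adds 6 × 25/8 = 18.75 to the sample variance. The test therefore uses a standard error of about √(39.0/9) = 2.08, although the true SD is 1.50.

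**5. Power for 6% by simulation, SD of difference 4.5%.** Random order with an unadjusted paired test, n = 8: about 90% at no shift, 86% at 2%, 80 to 82% at 3% and 67% at 5%. At a 5% shift:

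| Allocation and analysis | n = 8 | n = 9 |
|---|---|---|
| Random order, paired test | 67% | 73% |
| Latin blocks, paired test | 67% | 76% |
| Random order, visit term | 88 to 90% | 93% |
| Latin blocks, visit term | 93% | 96% |

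**6. Another form of visit effect.** With a steady drift per visit, SD of difference 4% and n = 8, random order with a paired test gives 94.9% (no drift), 93.0% (1% per visit), 84.9% (2%) and 70.2% (3%). Balance alone gives 86.4% at 2% and 72.7% at 3%. A visit term with random order gives 94.4% and 94.2%; both together give 96.8% and 96.7%. The mean estimate stays at 5.97 to 6.03 and type I error near 5% under random order.

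**7. Metabolic substudy.** Suppose the 10 are drawn from 20 allocated 10:10. A split of 7:3 or worse has probability 2 × (1 + 100 + 2025 + 14400)/184756 = 18%. Under simple randomisation it is 2 × (1 + 10 + 45 + 120)/1024 = 34%. At 7:3 the period-adjusted standard error grows by √[(1/7 + 1/3)/(1/5 + 1/5)] = 1.09. With the plan's SD of 8% and effect of 10%, power moves from about 93% at 5:5 to 89% at 7:3.

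**The case against.** The protocol is silent rather than wrong: a randomised Latin square would satisfy its description of the order, and its reference to appropriate paired tests does not exclude adjustment for visit. That stands, and the criticism is that balance and a visit term are not secured, not that they are ruled out.

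The visit effect is an assumption. That also stands: the documents give no size, and at a drift of 1% per visit the loss is only about 2 points. Change from the pre-dose value would remove a constant visit shift, but its use is not stated and it adds the noise of the baseline measurement.

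Three stronger readings are tempting, and the documents support none of them:
- A reader might infer that the product comparison is biased. It is not, on average; random order gives the right mean and a type I error near 5%.
- A reader might infer that balanced sequences alone would keep the power. They would not under an unadjusted paired test, as steps 4 and 5 show.
- A reader might infer that the product is chosen on the 6% cardiac-output contrast. Section 4 says only that the choice depends on the pilot's outcome. Venous 3-OHB is also a pilot endpoint, and uptake kinetics is the pilot's first stated purpose.

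On the metabolic group, Section 4 lets participants join one substudy only, so the 10 need not be a subset of the 20.

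**Conclusion.** The point holds as a modest design improvement. As written, the pilot secures neither balance over visit position nor a visit term. If a visit effect exists, it adds variance to the drink contrasts: at an assumed 5% first-visit shift, paired-test power at n = 8 falls from about 90% to 67%; at 2% it falls only to 86%. The visit term recovers most of this. Balance adds about 3 to 5 points on top at n = 8 and, without any model, reduces the SD of the estimate from 2.17 to 1.68 (n = 8) or from 2.03 to 1.49 (n = 9). That reduction is useful if the product is chosen from estimates rather than p-values. These figures rest on an additive visit effect of assumed size, an SD of the difference of 4.5%, and independent random orders. The metabolic part is a minor matter of precision and assumes that those 10 patients come from the 20.

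**What to change.** - State the sequence set, and allocate pilot patients in randomised blocks of three-drink Latin-square sequences. Plan 9 patients, so that each drink is given three times at each of visits 1, 2 and 3. A replacement should take the sequence of the patient replaced.
- In Section 6, prespecify a linear model with patient, visit and drink for the pilot's cardiac-output comparison, and say whether the pre-dose value is used.
- As a minor addition, randomise the KETO-CHF sequence in blocks stratified by metabolic-substudy participation, so that the 10 metabolic patients split 5:5. Table 1 places consent before randomisation, so participation can be known in time.

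The cost is a different randomisation list and a sentence or two in Section 6. With 9 patients and 27 measurements, the visit term takes error degrees of freedom from 16 to 14. No visits are added and the number stays within 8 to 10, although planning 9 leaves room for one replacement rather than two. Nine patients balance position but cannot fully balance which drink precedes which; that needs all six orders equally often, for example 12 patients.

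### The KETO-KINETICS pilot records cardiac output hourly on three drinks but pre-specifies no single summary per visit and no use of the pre-dose readings, which leaves hour-by-hour testing open and available precision unclaimed

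*Combined protocol and SAP*

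**What the plan says.** Section 4 (KETO-KINETICS) describes a three-period crossover of two ketone products and an isocaloric placebo, taken "in random order on 3 visits". The endpoint line reads "Endpoints: Cardiac output, venous 3-OHB levels, LVEF, LV global strain". None of the four is marked primary, whereas cardiac output is marked primary for KETO-CHF in the same section. On timing, the plan says "Swan-Ganz Monitoring, Echocardiography, ECG and blood pressure will be recorded hourly" and "Sampling will be performed hourly from 1 hour before till 5 hours after oral intake". That gives five post-dose readings per visit and one or two pre-dose readings: one at -1 h, and one at 0 h if it is taken before the drink.

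Section 6 (Power calculation and statistics) bases the pilot on cardiac output with a CV of 4%. It states for 8 patients that "we will be able to detect a relative difference of 6% with a power of 90" per cent, at a two-sided 5% level. The analysis rule is "Differences will be compared by appropriate paired statistical tests", with significance at p of 0.05 or less, plus a general remark that regression will be done. No time point, summary measure, baseline term or ordering of comparisons is given for the pilot.

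The KETO-CHF design paragraph in section 4 makes the product used in the main study depend on the pilot's outcome, without defining that outcome.

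**The concern.** A paired test needs one number per patient per drink. With five post-dose readings and no named summary, someone must choose which number to compare, and as written that choice can be made after the data are seen. Testing each hour at 5% is one analysis that the wording allows, and it raises the chance that some hour looks significant when nothing is happening.

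The pre-dose readings are a second matter. They are taken at every visit through an invasive catheter and can remove much of the visit-to-visit variation in cardiac output. The plan does not say whether they will be used.

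The pilot carries a formal power statement and feeds the choice of product that 20 patients will take for four weeks, so it is more than descriptive.

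**Working it through.** **Inputs.** From the documents: n = 8 (section 6: "In the pilot study we plan to include 8 patients"; the 10 in section 4 is covered by the stated allowance for drop-outs and missing values), CV 4%, difference 6%, power 90%, two-sided 5%, five post-dose hours, two active drinks and one placebo. Not in the documents: the correlation *r* between readings at the same visit. It is assumed and varied from 0 to 0.9. It equals the share of the 4% variation that is common to a whole visit.

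**1. The plan's own figure.** Paired t-test, noncentrality = 6 × √8 / SD of the difference.

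- If 4% is the SD of the paired difference: 6 × 2.83 / 4 = 4.24, power 95%; 90% power needs n = 7.
- If 4% is the CV of one reading: SD of the difference = 4 × √2 = 5.66%, noncentrality 3.0, power 73%; 90% power needs n = 12.
- Exactly 90% at n = 8 needs an SD of the difference of about 4.5%.

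Section 6 does not say which meaning applies.

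**2. False positives, cardiac output only.** Hour-by-hour testing gives 5 hours × 2 actives = 10 tests against a shared placebo. If they were independent, 1 − 0.95^10 = 40%. Simulated paired t-tests at n = 8:

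| *r* within visit | Chance of at least one false positive, 10 tests |
|---|---|
| 0 | 39% |
| 0.3 | 37% |
| 0.6 | 31% |
| 0.9 | 19% |

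With one summary per visit and two comparisons, independence gives 1 − 0.95² = 9.75%. With the shared placebo, simulation gives about 9%.

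**3. Precision.** Set the variance of a single post-dose hour to 1, with equal correlation *r* between all readings of a visit.

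- Mean of five hours: (1 + 4*r*)/5, which is 0.44 at *r* = 0.3 and 0.92 at *r* = 0.9.
- The same mean with one pre-dose reading as covariate: (1 + 4*r*)/5 − *r*². At *r* = 0.3 this is 0.44 − 0.09 = 0.35; at *r* = 0.9 it is 0.92 − 0.81 = 0.11.

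Simulated power at n = 8 for a 6% effect lasting all five hours, single-hour SD of the difference 5.66%, one pre-dose reading:

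| *r* | One hour | Five-hour mean | Five-hour mean, pre-dose covariate |
|---|---|---|---|
| 0.3 | 73% | 97% | 96% |
| 0.5 | 73% | 91% | 96% |
| 0.7 | 73% | 84% | 99% |
| 0.9 | 73% | 77% | 100% |

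With two pre-dose readings the last column is 98-100%. The type I error of each adjusted comparison in a patient-period-treatment model stayed near 5%. If the single-hour SD of the difference is 4%, one reading already has 95% power and the adjusted mean close to 100%.

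A simple change score is less safe than the covariate. With one pre-dose reading, change of the five-hour mean has variance 0.84 at *r* = 0.3, against 0.44 for the unadjusted mean; the two are equal at *r* = 0.5.

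**4. Effects that fade** (4% taken as the CV of one reading).

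- Effect falling from 6% to 1.2% over five hours: the 1-5 h mean has 81-97% power with the covariate and 45-73% without, for *r* of 0.25 to 0.75. At *r* = 0 the covariate costs a little (93% against 96%).
- A 6% effect lasting only two hours: the adjusted 1-5 h mean has about 40-75% power, against about 73% for a single hour correctly chosen in advance.

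**The case against.** The best reply is that the plan is silent rather than wrong. It nowhere says that every hour will be tested, it does not exclude a change or covariate analysis, and it mentions regression. This stands. A reader might infer that the plan prescribes hourly tests or discards the pre-dose readings; the documents support neither, and the ten-test count is one permitted analysis, not the stated one.

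The power statement rests on cardiac output, which implies a lead endpoint. That also stands, but it settles the endpoint and not the hour, and the 19-39% already counts cardiac output alone.

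It is tempting to read the 19-39% as the chance of taking the wrong product into KETO-CHF. It is not. It concerns active-versus-placebo tests when neither product works, whereas the choice lies between the two actives, and the plan does not say that significance decides it.

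The effect may be large: the background section cites a 40% rise in cardiac output during infusion. Even a 10% effect would give a single-reading test 99% power with the larger SD. Oral effects may be smaller, but it is fair to say that the precision gain matters mainly near the 6% the plan itself uses.

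Finally, a 1-5 h mean is a debatable window after one oral dose whose kinetics are still to be learned. That is a real trade-off. It argues for care in choosing the window, and not for leaving it open.

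**Conclusion.** The omission is confirmed. The pilot analysis fixes no post-dose summary, no use of the pre-dose readings and no order of comparisons. If cardiac output were tested hour by hour, the chance of at least one false positive would be about 19-39% at n = 8, against about 9% with one summary and two comparisons. For a sustained 6% effect, power would rise from 73% to about 96-100% if 4% is a single-reading CV, and from 95% to nearly 100% if it is the SD of the paired difference.

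These sizes rest on an assumed within-visit correlation (0 to 0.9 for false positives, 0.3 to 0.9 for power) and on 4% covering all day-to-day variation within a patient, which the documents do not establish.

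Two stronger readings should be resisted. One summary does not remove the multiplicity, because two tests at 5% remain unless they are ordered. Nor is the pilot shown to miss its 90% power, because that depends on the unstated meaning of the 4%. The point is a pre-specification gap worth closing, because the pilot's result steers the main study.

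**What to change.** Add to section 6, before any pilot data are seen:

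- Cardiac output is the pilot's lead endpoint.
- Each visit contributes one post-dose value: a mean or area under the curve over a stated window, such as 1-5 h.
- That value is analysed with the visit's pre-dose mean as covariate, in a model with patient, period and treatment.
- The two active-versus-placebo tests are made in a stated order, the second being confirmatory only if the first succeeds.
- The direct comparison of the two products is reported with a confidence interval, since the pilot chooses between them.
- Hourly values, LVEF and strain are descriptive.

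The cost is analysis wording only; no patients, visits or measurements are added. There are two downsides. A long window dilutes a short effect (about 40-75% power if a 6% effect lasts two hours, against about 73% for a correctly chosen hour). The covariate uses one degree of freedom and brings little or no gain if readings within a visit are uncorrelated.

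### Does Table 1, with second examinations at weeks 10-12, contradict the four weeks stated for each drink?

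*Combined protocol and SAP*

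**What the plan says.** Objective 3 (section 3) sets the target: "To investigate the effect of 4 weeks modulation of circulating ketone body levels on cardiac function", together with exercise capacity. The KETO-CHF design paragraph in section 4 repeats the duration for both arms: "Patients are studied after 4 weeks of oral 3-OHB three times daily" "and 4 weeks isocaloric placebo-drink".

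Table 1 gives the calendar. Randomization and delivery are at V1, time 0. The first hemodynamic and metabolic examinations, V2 and V3, share a window of 3-5 weeks. The one crossover mark stands under V3. The second round, headed "V4 Hemodynamic examinations 2" for V4 and followed by metabolic visit V5, has a window of 10-12 weeks.

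Three other statements bear on the point.
- Section 4 makes the substudies separable: "Thus participants can opt only to participate in one substudy if they prefer".
- Section 6 plans the hemodynamic comparison "by enrolling 20 patients in the hemodynamic examinations", whereas "10 patients will be included in the metabolic studies".
- Table 2, for the hemodynamic study day, has a row for "3-OHB/placebo ingestion".

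The available text and tables mention no washout, pause or start date for the second period. Figure 1, the flowchart placed just before Table 1, is not reproduced in the text reviewed.

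**The concern.** Read literally, the crossover mark at V3 means that patients change drink at weeks 3-5 and are next examined at weeks 10-12. The second period would then be clearly longer than the first and longer than the four weeks stated. Each patient's paired difference in cardiac output would compare a shorter exposure to one drink with a longer exposure to the other, and the average would not be the four-week effect in Objective 3. Randomized order keeps this from favouring one drink, but it would change what is estimated.

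If four weeks is kept instead, there must be a gap between the periods. In a crossover trial that gap is part of the protection against carryover, so a reader wants to see its length. Section 6 names only paired tests, with no period or carryover term to fall back on.

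The crossover mark also stands only under a metabolic visit, and many of the patients in the primary comparison need not attend one.

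**Working it through.** **Inputs.** Stated duration per drink: 4 weeks (Objective 3, section 4). From Table 1: randomization at 0; first examinations and crossover mark at 3-5 weeks (midpoint 4); second examinations at 10-12 weeks (midpoint 11). Section 6: 20 hemodynamic and 10 metabolic patients.

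**First period.** Examination minus randomization = (3 to 5) − 0 = 3 to 5 weeks, midpoint 4. This reproduces the stated duration with a tolerance of one week either way.

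**Second period, if the new drink starts at the crossover mark.** Shortest: 10 − 5 = 5 weeks. Longest: 12 − 3 = 9. Midpoints: 11 − 4 = 7. No combination gives exactly 4. Only one corner (crossover at week 5, examination at week 10) falls inside the 3-5 weeks accepted for the first period. With equal numbers in the two sequences, which is an assumption, the average duration behind the contrast would be (4 + 7)/2 = 5.5 weeks, or 1.5 more than stated.

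**Second period, if four weeks is kept.** Let s be its start. Centring the second examinations on four weeks gives s = 11 − 4 = 7. Exposure at V4 and V5 is then 10 − 7 = 3 to 12 − 7 = 5 weeks, the same 4 ± 1 as in the first period. The interval is 7 − 4 = 3 weeks at midpoints.

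**Spread of that interval.** With s held at week 7 and the first drink stopped at the first examinations, it runs from 7 − 5 = 2 to 7 − 3 = 4 weeks. The wider range of 1 to 5 comes from 10 − 4 − 5 = 1 and 12 − 4 − 3 = 5. That fixes second-period exposure at exactly 4 weeks and pairs opposite window limits, although the first period is allowed a week either way.

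**Other ways to fill the gap.** The run-in in section 9 lasts four days and precedes randomization, so it cannot account for the time between V3 and V4.

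**Crossover mark.** At least 20 − 10 = 10 hemodynamic patients may have no V3. But V2 and V3 share one window, and V3 is the last first-period column in a table that covers both substudies. Its position fits a switch once the first-period examinations are complete.

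**The case for a change.** The strongest case for acting is that the subtraction is correct and nothing visible resolves it. Text and table agree only if an interval is supplied that no available sentence mentions. Duration cannot be assumed irrelevant either, since section 1 says that no data exist on oral supplementation in chronic heart failure. And writing the schedule out would cost almost nothing.

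Part of this stands. The interval and the start of the second period are absent from the available text, and the switch time for patients who attend only hemodynamic visits has to be inferred. Objective 3, section 4 and Table 1 need to be read together and reconciled when the schedule is next written out; no duration or switching rule is suggested here.

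The statistical harm does not follow. The 5.5-week average arises only on the reading that contradicts section 4. The carryover worry is limited by the calendar: if the first drink stops at the crossover mark, the second examination comes at least 5 weeks later, and about 7 at midpoints, on either reading. The figure of half the patients lacking a crossover visit describes the layout of a table, not patients without a switch time. Ingestion on the hemodynamic study day may add an acute component under either reading, so it does not separate them.

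**Conclusion.** The concern does not call for a change to the plan. The mismatch is real as arithmetic: about 7 weeks (5 to 9) from crossover mark to second examination against a stated 4. One reading satisfies every statement together, with 3 to 5 weeks of exposure at examination in both periods and about 3 weeks between them. Followed that way, the trial gives the four-week paired contrast that Objective 3 asks for. What is left is a missing detail, the start of the second period, which trial staff can fill from the stated four weeks.

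This rests on three assumptions: that the four weeks in Objective 3 and section 4 govern; that the Table 1 windows are visit tolerances; and that a start at about week 7, which is inferred, is what was meant. Figure 1 could confirm or correct the last. If it showed instead that the second drink starts at V3, the unequal-duration question would reopen. Its size still could not be computed, because the documents do not say how the effect changes between 4 and 7 weeks.
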